The PREVAIL intervention consists of weekly interactions over the course of 3-months using a flexible approach to accommodate Veteran's preferences and recovery needs over the course of the typical duration of a PRF. During weeks 1 and 2 of the intervention, Veterans meet twice weekly with a PS. During weeks 3 through 8, meetings are once weekly. During weeks 9 through 12, meetings typically occur once every other week. Over the course of the 3-month intervention, this approach bolsters the development of a strong therapeutic alliance in the beginning (weeks 1-2), followed by active teaching and reinforcing new skills (weeks 3-8), and then culminating with mastering new skills and preparing the Veteran for active self-management and sustained recovery. For a small number of PREVAIL participants, an additional 3 sessions were added over the span of the last 4 weeks to provide additional time to prepare for the end of the therapeutic relationship. A similar approach will be used for the current pilot.

Meetings between PSs and Veterans will be approximately 45-60 minutes and occur primarily in the community, home, clinic, by telephone, or VA-approved video calling platform (e.g. VVC, WebEx). Session content will be rooted in PSs offering nonjudgmental empathic support, active listening, and constructive disclosure and role modeling. A primary focus will be helping patients with PRFs to identify and strengthen connections with informal supports and participation in activities in their community that will enable them to feel more worthwhile as individuals and hopeful about their future.

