Participants will be instructed on how to contact the crisis hotlines, emergency services, or closest emergency department if they are experiencing a suicidal crisis. Peer specialists and study team members are not to further assess or manage suicide risk beyond the established protocol. Participants will be instructed to contact their clinicians or the Suicide Prevention Coordinator. All outgoing voicemail messages on VA Connecticut phone lines are mandated to include instructions on how to contact crisis services. Due to policies associated with COVID-19, most meetings between peer specialists and participants will occur onsite at VA facilities in person or via VA Video Connect or WebEx during business hours. On the off chance that meetings occur outside of regular business hours, clinician back up will be prearranged. Written safety procedures for conducting community-based meetings include use of public locations, during daylight hours, and mandatory call-in procedures. In our prior research, using such procedures with similar populations, no incidents where staff safety concerns became an issue occurred during follow-up assessments. All safety concerns will be reported immediately to the PI.

Fidelity to the PREVAIL model will be evaluated by 'blinded' raters independent of the research team after participants complete their post-intervention assessment interview. A 20% random sample of audio recorded sessions will be assessed in terms of adherence to PREVAIL principles (i.e., interactions that follow the format of Invite, Share, Learn, Motivate) and assessment of suicidal ideation as well as demonstration of general support skills.

Benefits

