5.2 Recruitment Methods

Recruitment-Aim 1

We will recruit a diverse group of 12 individuals for the Needs Assessment phase of the project to inform the adaptation of PREVAIL. This group will be comprised of Veterans (3), Peer Specialists (3), Providers from behavioral health, inpatient and outpatient psychiatry, and other relevant departments (4), and Clinical Directors (2).

We will obtain a waiver of HIPAA authorization to identify Veterans to participate in the Needs Assessment. Once these Veterans are identified, they will be mailed a letter informing them about and requesting their participation in the Needs Assessment interviews. A member of the study team will follow-up with a telephone call approximately one week after the letter is sent. The team members will attempt to reach the Veterans by phone 3 times and will leave no more than two messages. Providers, clinical directors, and Peer Specialists will either be sent an email or will be verbally invited in person to participate in the Needs Assessment.

Recruitment for the Steering Committee

The Steering Committee will be comprised of researchers and VHA leadership. The site PI will identify appropriate VA staff and other providers and will contact them by phone or email.

Recruitment-Aim 2

We will recruit 4-6 Peer Specialists who are currently working in VA Connecticut Healthcare System (VACT) to receive training in the PREVAIL model and to deliver the intervention for the pre- and formal pilot. All of the selected Peer Specialists have been trained and certified, with multiple years of clinical experience working with Veterans in recovery, including those who have been at some point 'flagged' for suicide risk.

We will include a sample of up to 24 VHA patients identified as being high-risk for suicide at the VA Connecticut Healthcare System (VACT) to receive the pilot intervention as an adjunct to usual care. Patients will be considered high suicide risk if they have a Patient Record Flag (PRF) in their medical chart for a recent suicide attempt, serious suicidal ideation, or other warning signs of acute suicide risk. The VACT Suicide Prevention Coordinator maintains a list of patients with active PRFs. This population is targeted because they are at greatest risk for suicide and therefore most in need of intervention.

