In addition to reaching out to Veterans on the high-risk list, we also will engage Veterans via the New Haven VA psychiatric Emergency Room, inpatient units, and individual New Haven clinicians. Specifically, we will engage with staff to find out if any Veteran has received a score on the Columbia-Suicide Severity Rating Scale Screen of 3 or greater in the last three months. This measure is used commonly in the VA. Such a score is known to be an optimal cut off score for identifying individuals who would likely attempt suicide. In a recent study of nearly 19000 patients, those scoring over the cut-off of ≥ 3 had almost four times the odds of dying by suicide within 1 week and 1 month, respectively, and doubled the odds of dying within a year⁹⁰. We will also engage with individual clinicians to assess whether any of their patients have recently received a score of ≥ 3 on the Columbia measures. In addition, we will ask these staff about any Veteran who made a suicide attempt in the last three months. Thus, the additional recruitment criteria we are adding will be:

- Any Veteran from the New Haven VA psychiatric Emergency Room, the New Haven inpatient units, or from individual New Haven clinicians who received a score on the Columbia-Suicide Severity Rating Scale Screen of 3 or greater in the last three months
- Any Veteran from the New Haven VA psychiatric Emergency Room, the New Haven inpatient units, or from individual New Haven clinicians who made a suicide attempt within the last three months

Each month, there are approximately 105 VHA patients with PRFs for suicide risk at the CT VA campuses. In addition to those Veterans with a PRF, we also will be recruiting those Veterans with suicidal ideation or attempts. This pool of Veterans should be sufficient to recruit participants for the pre-pilot (n=12) and formal pilot (n=12). Assuming a 75% retention rate (as achieved in [name] PREVAIL pilot)¹⁵ this will yield a final sample of 18 patients with outcome data at post-intervention and 3-month follow-up. This sample size will yield reasonably precise estimates of feasibility in terms of actual rates of recruitment, retention, compliance/fidelity to intervention, and completion of outcome assessments.

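### Fidelity is rated on a 20% random sample with no stated stratification by Peer Specialist or session phase, and its claimed precision rests only on a patient count

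*Protocol*

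**What the plan says.** The fidelity check is described at the end of the Data Safety and Monitoring plan in Protocol section 5.1. Blinded raters from outside the research team work from session recordings: "A 20% random sample of audio recorded sessions will be assessed in terms of adherence to PREVAIL principles". They also rate whether suicidal ideation was assessed and whether general support skills were shown. The draw is called random; no stratification by Peer Specialist, Veteran or phase is mentioned.

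Section 5.2 plans four to six Peer Specialists to deliver both pilots, and on the patient side: "We will include a sample of up to 24 VHA patients identified as being high-risk for suicide".

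Section 5.1 sets out three phases of contact. The first is the densest: "During weeks 1 and 2 of the intervention, Veterans meet twice weekly with a PS". The second runs to week 8 with one session a week. The third is the sparsest: "During weeks 9 through 12, meetings typically occur once every other week". In the earlier PREVAIL work a few participants had more: "an additional 3 sessions were added over the span of the last 4 weeks". A similar approach is planned here.

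Section 5.2 then claims: "This sample size will yield reasonably precise estimates of feasibility in terms of actual rates of recruitment, retention, compliance/fidelity to intervention". The only figure behind that sentence is the expected 18 Veterans with outcome data. Section 5.6 plans descriptive statistics and confidence intervals. The SAP covers descriptive statistics and the Reliable Change Index for each participant. Neither says how fidelity will be summarised.

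**The concern.** Following the four-step session format is largely something the Peer Specialist does, so sessions delivered by the same person may resemble each other. If they do, the number of Veterans does not determine how well fidelity is known; the number of Peer Specialists matters more.

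Two things are at stake. First, a draw that ignores Peer Specialist and phase can miss some combinations altogether. Weeks 9-12 are the most exposed because they hold the fewest sessions, and that is the phase in which the Veteran is prepared for self-management and the end of the relationship. Second, the pilot is meant to inform a multi-site randomised trial staffed by other Peer Specialists. A fidelity figure carried forward as precise because 24 Veterans were enrolled would claim more than four to six providers can support.

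**Working it through.** **Plan's own figure.** 24 Veterans × 75% retention = 18, as section 5.2 states. No interval width, fidelity rate or intraclass correlation (ICC) is given there.

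**Sessions rated.** From the section 5.1 schedule:
- weeks 1-2: 2 × 2 = 4; weeks 3-8: 6 × 1 = 6; weeks 9-12: 4 / 2 = 2; total 12 per Veteran
- 24 × 12 = 288 sessions; 20% = 57.6, about 58
- if only 18 Veterans had full sessions: 18 × 12 × 0.2 = 43
- if all 24 had the 3 extra sessions: 24 × 15 × 0.2 = 72

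**Coverage of phases under an unstratified draw.** Assume equal caseloads, all sessions recorded, and 58 drawn from 288. Weeks 9-12 contain 24 × 2 = 48 sessions, so each of k Peer Specialists has c = 48/k of them. The chance that one given Peer Specialist has none rated is C(288 − c, 58) / C(288, 58). The chance that at least one has none follows by inclusion-exclusion: the sum over j = 1 to k of (−1)^(j+1) · C(k, j) · C(288 − cj, 58) / C(288, 58).

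| k | c | one given specialist | at least one |
|---|---|---|---|
| 4 | 12 | 6.3% | 23% |
| 6 | 8 | 16.1% | 66% |

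This needs no assumption about adherence or ICC. Over all phases together the draw is less uneven: 95% ranges of 9 to 20 rated sessions per Peer Specialist (k = 4) or 5 to 15 (k = 6).

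**Precision of an overall adherence rate.** Assumptions not in the documents: a yes/no rating, p = 0.80, ICC from 0 to 0.20, equal clusters, 95% level.
- Sessions treated as independent: 1.96 × √(0.8 × 0.2 / 58) = 10.3 points.
- Clustered: multiply the variance by the design effect DE = 1 + (58/k − 1) × ICC.

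| k | ICC | DE | effective sessions | half-width (z) | half-width (t, k − 1 df) |
|---|---|---|---|---|---|
| 6 | 0.05 | 1.43 | 41 | 12.3 | 16.2 |
| 6 | 0.10 | 1.87 | 31 | 14.1 | 18.4 |
| 6 | 0.20 | 2.73 | 21 | 17.0 | 22.3 |
| 4 | 0.05 | 1.68 | 35 | 13.3 | 21.6 |
| 4 | 0.10 | 2.35 | 25 | 15.8 | 25.6 |
| 4 | 0.20 | 3.70 | 16 | 19.8 | 32.2 |

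At ICC = 0 the design effect is 1 and there is no penalty.

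**The target matters.** If the aim is only to describe the 288 sessions delivered, a simple random sample needs no clustering penalty. With the finite-population correction the half-width is 1.96 × √(0.16 / 58 × 0.8) = 9.2 points. In a beta-binomial simulation at ICC 0.1, 0.2 and 0.3 with 4 × 14 sessions, an exact 95% session-level interval covered the population rate in about 81%, 70% and 61% of runs. It covered the mean of the specialists actually studied in 97-98%.

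**The case against.** A reader might infer that the plan specifies a session-level fidelity interval that is too narrow, or that its precision claim is demonstrably overstated. The documents support neither reading. The intervals in section 5.6 are described for the measures at each assessment period, and fidelity is not among the measures in section 5.5. The precision sentence gives no width to test, and its wording could include Veteran-level compliance. The sampling is called random, not simple random; silence on stratification does not show that none will be used. Section 4.0 was not in the text available for this review.

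The sizes also rest on assumed adherence and ICC, and the penalty vanishes at ICC zero or when only the studied specialists are described. The protocol lets the Veteran ask for more or less structure, so part of the variation in adherence may lie with the Veteran. Weekly supervision, with invited sharing of recordings, is a separate way to notice a weak specialist. Finally, the stated go criteria are more than 50% enrollment and more than 70% follow-up completion; nothing in either document turns on a fidelity interval.

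All of this stands, and it limits the point to an unspecified summary and an unsupported precision statement. It does not answer the gap in phase coverage, which is independent of the ICC. Nor does it make a patient count a basis for provider-level precision in a later trial.

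**Conclusion.** The point holds as a low-cost improvement of modest consequence. If the draw is unstratified and caseloads are equal, the chance that at least one Peer Specialist has no rated session from weeks 9-12 is about 23% with four specialists and 66% with six. For generalising beyond these specialists, an interval that treats sessions as independent would be too narrow for any positive ICC: 10 points against about 12 to 20 at ICC 0.05 to 0.20, or about 16 to 32 with t on three to five degrees of freedom. These widths assume 80% adherence and a yes/no rating. For describing only the pilot's own specialists or sessions, the session-level interval is adequate. The precision claim for fidelity is therefore unsupported, not shown to be wrong.

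**What to change.** 1. In section 5.1, draw the same 20% within each Peer Specialist and phase (weeks 1-2, 3-8, 9-12), with at least one session per cell.
2. In section 5.6 and the SAP, name the unit of the fidelity summary and report adherence for each Peer Specialist, with the range.
3. Give any overall interval either as describing the studied specialists only, or in a cluster-aware form with a note that four to six clusters make it approximate. A t interval on the specialist means is not a full cure: in the same simulations it covered only about 87-92% at ICC 0.1 to 0.3.
4. In section 5.2, remove fidelity from the precision sentence, or qualify it.

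Cost: small rounding in the number of rated sessions. With four specialists the cells hold 24, 36 and 12 sessions, so 20% rounds to 5 + 7 + 2 = 14 each, 56 in all. With six they hold 16, 24 and 8, giving 3 + 5 + 2 = 10 each, 60 in all, against 58 now. Cells in weeks 9-12 remain thin at about two sessions, and a specialist with few cases still gets few ratings. The precision statement becomes less favourable.

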5.2 Recruitment Methods

Recruitment-Aim 1

We will recruit a diverse group of 12 individuals for the Needs Assessment phase of the project to inform the adaptation of PREVAIL. This group will be comprised of Veterans (3), Peer Specialists (3), Providers from behavioral health, inpatient and outpatient psychiatry, and other relevant departments (4), and Clinical Directors (2).

We will obtain a waiver of HIPAA authorization to identify Veterans to participate in the Needs Assessment. Once these Veterans are identified, they will be mailed a letter informing them about and requesting their participation in the Needs Assessment interviews. A member of the study team will follow-up with a telephone call approximately one week after the letter is sent. The team members will attempt to reach the Veterans by phone 3 times and will leave no more than two messages. Providers, clinical directors, and Peer Specialists will either be sent an email or will be verbally invited in person to participate in the Needs Assessment.

Recruitment for the Steering Committee

The Steering Committee will be comprised of researchers and VHA leadership. The site PI will identify appropriate VA staff and other providers and will contact them by phone or email.

Recruitment-Aim 2

We will recruit 4-6 Peer Specialists who are currently working in VA Connecticut Healthcare System (VACT) to receive training in the PREVAIL model and to deliver the intervention for the pre- and formal pilot. All of the selected Peer Specialists have been trained and certified, with multiple years of clinical experience working with Veterans in recovery, including those who have been at some point 'flagged' for suicide risk.

We will include a sample of up to 24 VHA patients identified as being high-risk for suicide at the VA Connecticut Healthcare System (VACT) to receive the pilot intervention as an adjunct to usual care. Patients will be considered high suicide risk if they have a Patient Record Flag (PRF) in their medical chart for a recent suicide attempt, serious suicidal ideation, or other warning signs of acute suicide risk. The VACT Suicide Prevention Coordinator maintains a list of patients with active PRFs. This population is targeted because they are at greatest risk for suicide and therefore most in need of intervention.

In addition to reaching out to Veterans on the high-risk list, we also will engage Veterans via the New Haven VA psychiatric Emergency Room, inpatient units, and individual New Haven clinicians. Specifically, we will engage with staff to find out if any Veteran has received a score on the Columbia-Suicide Severity Rating Scale Screen of 3 or greater in the last three months. This measure is used commonly in the VA. Such a score is known to be an optimal cut off score for identifying individuals who would likely attempt suicide. In a recent study of nearly 19000 patients, those scoring over the cut-off of ≥ 3 had almost four times the odds of dying by suicide within 1 week and 1 month, respectively, and doubled the odds of dying within a year⁹⁰. We will also engage with individual clinicians to assess whether any of their patients have recently received a score of ≥ 3 on the Columbia measures. In addition, we will ask these staff about any Veteran who made a suicide attempt in the last three months. Thus, the additional recruitment criteria we are adding will be:

- Any Veteran from the New Haven VA psychiatric Emergency Room, the New Haven inpatient units, or from individual New Haven clinicians who received a score on the Columbia-Suicide Severity Rating Scale Screen of 3 or greater in the last three months
- Any Veteran from the New Haven VA psychiatric Emergency Room, the New Haven inpatient units, or from individual New Haven clinicians who made a suicide attempt within the last three months

Each month, there are approximately 105 VHA patients with PRFs for suicide risk at the CT VA campuses. In addition to those Veterans with a PRF, we also will be recruiting those Veterans with suicidal ideation or attempts. This pool of Veterans should be sufficient to recruit participants for the pre-pilot (n=12) and formal pilot (n=12). Assuming a 75% retention rate (as achieved in [name] PREVAIL pilot)¹⁵ this will yield a final sample of 18 patients with outcome data at post-intervention and 3-month follow-up. This sample size will yield reasonably precise estimates of feasibility in terms of actual rates of recruitment, retention, compliance/fidelity to intervention, and completion of outcome assessments.

Once eligible Veterans are identified, they will be mailed a letter along with a study information sheet, inviting them to participate in Aim 2 of study. A member of the study team will follow-up with a telephone call approximately one week after the letter is sent if they do not hear back from the Veterans. The team members will attempt to reach

the Veterans by phone 3 times and will leave no more than two messages.

Additionally, the site PI will work with providers of eligible Veterans seeking their help in recruiting these Veterans into the study and will also provide them with a study information sheet. Once the provider identifies an eligible Veteran, they will discuss the study with the Veteran and if the Veteran is interested in hearing more about the study, the provider will call the study staff with the Veteran present or will share the number of the study staff with the Veteran so that they may call the study staff at their own convenience. In the event that the provider facilitates the phone call with study staff, the provider will step out of the room to give the Veteran a chance to learn more about the study. for this to occur. If a provider or research staff cannot reach the Veteran by phone, they will follow-up with a CIRB-approved letter as described above.

Version 4.0 Suicide Prevention Protocol Page **20** of 36

Payments

Veterans who participate in the Needs Assessment interview will receive \$25 for their time and effort. Study participants will receive \$25 upon completion of each assessment interview (baseline, post-intervention, 3-month follow-up), for a total of up to \$75. Additionally, Veterans who participate in the one-time interview will receive \$25 for their time and effort.

5.3 Informed Consent Procedures

Veterans

Needs Assessment

Pursuant to a Waiver of HIPAA Authorization, the site PI will identify three Veterans appropriate for the Needs Assessment in discussion with clinical providers. Selected Veterans will be mailed a letter describing the participation and requesting that the Veteran respond about their interest by calling the number provided or mailing back the return letter in the stamped envelope provided. If the Veteran is interested in participating in the Needs Assessment, a member of the research team will arrange a time to discuss the study with them and obtain their written consent. The member of research team will then conduct the Needs Assessment interview following written consent or will schedule a mutually agreed upon time to conduct the interview.

Pre-Pilot and Formal Pilot

A face-to-face meeting (interview and/or focus groups) will be held with Peer Specialists who have been selected to participate in the proposed study. Research staff will obtain verbal consent, including the permission to obtain audio-recordings of interviews and/or focus groups conducted after they have completed training in the PREVAIL approach as well as after the pre-pilot to inform potential modifications to the intervention.

A face-to-face meeting will be held for Veterans who have been selected to participate in the pre-pilot and formal-pilot phases of the study. Research staff will administer written

informed consent (or Veteran assent along with consent of a conservator if applicable) and HIPAA authorization, including the permission to obtain audio- recordings, at the baseline visit. The ICF, HIPAA and other study materials will be submitted and approved by the CIRB prior to the start of any recruitment for the pre-pilotor pilot.

VA Staff

Needs Assessment Staff Interviews

Pursuant to a waiver of documentation of ICF for staff who are going to be interviewed for the Needs Assessment, a member of the research staff will read through the ICF for staff over phone, obtain verbal consent from the staff member, and record the name of the staff member and date of consent for tracking purposes.

Peer Specialist Interviews and/or Focus Groups

Pursuant to a waiver of documentation of ICF for Peer Specialists who are going to be interviewed via a 1:1 interview and/or focus group following their participation in the PREVAIL training as well as after the pre-pilot, a member of the research staff will read through the ICF for staff over phone or via MS Teams, obtain verbal consent from the staff member, and record the name of the staff member and date of consent for tracking purposes.

